Only adjudicated endpoints will be counted in the primary analysis. The “adjudicated endpoint” refers to an endpoint and date of the endpoint that has been confirmed by an independent adjudication committee who has no access to the treatment code. According to the information from the endpoint adjudication committee, the following rules will be applied to determine if an event reported in eCRF should be considered valid for the analysis or not:

Table 5.2-1: Rule for inclusion of events into the analysis

Included in the analysis	
WHF/death reported in the dedicated page of the eCRF and confirmed by adjudication committee	YES
WHF/death reported in the dedicated page of the eCRF and NOT confirmed by adjudication committee	NO

If more than one in-hospital WHF occurred, the first one will be used as the event. Censoring and time will be defined according to the following rule:

Table 5.2-2: Censoring and time rules

	Status	Time
At least one in hospital WHF and/or death occurred and:		
Difference between date and time of first occurrence of WHF/death and date and time of randomization +1 minute >120 hours	Censored	120h
Difference between date and time of first occurrence of WHF/death and date and time of randomization +1 minute \leq 120 hours	Event	Calculated difference
No in hospital WHF and death occurred and:		
Difference between date and time of last assessment* and date and time of randomization +1 minute >120 hours	Censored	120h
Difference between date and time of last assessment* and date and time of randomization +1 minute \leq 120 hours	Censored	Calculated difference

* Last assessment is the date and time of last available post-baseline physician assessment of in-hospital WHF

In case a patient is lost to follow-up, events occurring prior to the time of lost to follow-up will be counted. If no event occurred, then the patient will be censored at the time of last post-baseline in-hospital WHF assessment available.

The primary statistical hypothesis is:

	Statistical Analysis Plan
	Sponsor: NOVARTIS Protocol number: CRLX030A3301

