The time to in-hospital WHF/all cause death/readmission will be computed as the number of hours from randomization to the earlier of the onset of in-hospital WHF or death or readmission for heart failure plus 1 minute. The onset of in-hospital WHF through Day 14 will be the start date/time of event reported at the first assessment point at which the investigator reported worsening heart failure (either during the initial hospitalization or re-hospitalization for heart failure); if death occurred, date and time are reported in the dedicated eCRF section "Death – (Endpoint to be adjudicated)"; the date and time of admission of first re-hospitalization with Primary reason for Hospitalization equal to "Heart Failure" will be considered as the readmission moment (as reported in the dedicated eCRF section "Rehospitalization Information (Endpoint not to be adjudicated)"). Subjects without an event will be censored at the earlier of the last post-baseline assessment or 336 hours after randomization. Subjects without any information after baseline (i.e., randomization) will be considered censored at 1 minute.

	Statistical Analysis Plan
	Sponsor: NOVARTIS
	Protocol number: CRLX030A3301

In case of missing time of in-hospital WHF or death or rehospitalisation for heart failure then 00:00 will be imputed.

According to the information from the endpoint adjudication committee, the following rules will be applied to determine if an endpoint reported in eCRF should be considered valid for the analysis or not:

Table 5.2-3: Rule for inclusion of events into the analysis

	Included in the analysis
WHF/death occurred within Day 5, reported in the dedicated page of the eCRF and confirmed by adjudication committee	YES
WHF/death occurred within Day 5, reported in the dedicated page of the eCRF and NOT confirmed by adjudication committee	NO
WHF/death occurred after Day 5 through Day 14 and reported in the dedicated page of the eCRF	YES
Readmission for heart failure reported in the dedicated page of the eCRF	YES

Censoring and time will be defined according to the following rule:

Table 5.2-4: Censoring and time rules

	Status	Time
At least one in hospital WHF/death/readmission for HF occurred and: Difference between date and time of first occurrence of WHF/death/readmission for HF and date and time of randomization +1 minute >336 hours	Censored	336h

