Difference between date and time of first occurrence of WHF/death/readmission for HF and date and time of randomization +1 minute ≤336 hours	Event	Calculated difference
No in hospital WHF/death/readmission for HF occurred and: Difference between date and time of last assessment* and date and time of randomization +1 minute >336 hours	Censored	336h
Difference between date and time of last assessment* and date and time of randomization +1 minute ≤336 hours	Censored	Calculated difference

* Last assessment is the date and time of last available post-baseline physician assessment of in-hospital WHF

In case a patient is lost to follow-up, only the data until the last post-baseline in-hospital WHF assessment available will be considered in the analysis.

Treatment groups will be compared with a Gehan's generalized Wilcoxon test. The Kaplan-Meier estimates of the survival functions for each treatment group will be plotted. The Kaplan-

	Statistical Analysis Plan
	Sponsor: NOVARTIS Protocol number: CRLX030A3301

Meier estimates of the cumulative event rate will also be presented in tables by treatment group for each day and also by time interval (>0-5 days, >5-14 days).

Absolute frequencies and proportions of patients with event (as defined in the time to event analysis), overall (in-hospital WHF/all cause death/readmission) and by type of event (in-hospital WHF; all cause death; readmission), through Day 14 in each treatment group will also be provided (percentages based on population of analysis).

In addition, a description of all in-hospital WHF that occurred through Day 14 will be provided: absolute frequencies and proportions of patients with in-hospital WHF at each assessment time point will be presented overall and by the concomitant medication given (new, restarted or increased dose of medication), and/or by the need of mechanical/surgical intervention (yes/no) for the in-hospital WHF.

A summary of number and percentage of patients with or without WHF events through Day 5 (recorded on “Clinical worsening of heart failure” eCRF page for adjudicated events), and from Day 6 through Day 14 (recorded on “Heart failure details” eCRF page for events not to be adjudicated), will be provided by treatment.

Persistent signs or symptoms of HF/ non-improvement

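### Day 14 composite: read literally, the SAP's lost-to-follow-up sentence censors recorded heart failure readmissions that its own tables count as events

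*SAP*

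**What the plan says.** All of the following is in SAP section 5.2 unless stated otherwise.

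- **Which events count (Table 5.2-3).** The row "Readmission for heart failure reported in the dedicated page of the eCRF" is marked YES, without conditions.
- **How a readmission is dated.** The time is "the date and time of admission of first re-hospitalization with Primary reason for Hospitalization equal to" heart failure, taken from the re-hospitalization page of the eCRF. It does not depend on any WHF assessment.
- **Status and time (Table 5.2-4).** The row "Difference between date and time of first occurrence of WHF/death/readmission for HF and date and time of randomization +1 minute ≤336 hours" gives an event at its own time. The last assessment sets the time only in the rows that begin "No in hospital WHF/death/readmission for HF occurred and: Difference between date and time of last assessment* and date and time of randomization". The footnote defines it: "Last assessment is the date and time of last available post-baseline physician assessment of in-hospital WHF".
- **Loss to follow-up, Day 14 endpoint.** The sentence directly below that footnote says "only the data until the last post-baseline in-hospital WHF assessment available will be considered in the analysis".
- **Loss to follow-up, primary Day 5 endpoint.** Here "events occurring prior to the time of lost to follow-up will be counted", and censoring at the last WHF assessment applies only if there was no event.
- **Protocol section 9.5.1.** For the Day 14 composite, only patients without an event are censored. There is no separate rule for patients lost to follow-up.

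**The concern.** The SAP gives two instructions for the same patient. Table 5.2-4 first asks whether an event occurred and turns to the last WHF assessment only if none did. The sentence below it first cuts the data at the last WHF assessment, whatever is on record after that.

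The difference matters because of the visit schedule. WHF is assessed daily in the index stay, at Day 5 and at discharge, and then not until Day 14. HF readmission is the component added for this endpoint, and it comes after discharge, when no further assessment may be scheduled before Day 14. Protocol section 5.5.11 also tells sites to ask the patient, family or family physician about hospitalizations when follow-up is lost. A readmission can therefore be in the database with a date later than the last WHF assessment.

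At stake are the event count of a secondary endpoint, its Kaplan-Meier and Gehan-Wilcoxon results, and the Day 14 event proportions. The proportions use the events of the time-to-event analysis and take the analysis population as denominator. As written, the programmer would have to choose between the two instructions.

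**Working it through.** The documents give no figure to reproduce. No loss-to-follow-up rate is stated, and the sample-size text is blacked out in the public copy. The check is therefore to apply both rules to the same hypothetical patients, followed by an illustration of size.

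**Step 1. The two rules side by side.** Times are from randomization; the SAP adds 1 minute.

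| Patient, later lost to follow-up | Table 5.2-4 | Lost-to-follow-up sentence, read literally |
|---|---|---|
| Last WHF assessment 144 h (Day 6 discharge), HF readmission recorded at 216 h | Event at 216 h + 1 min | Censored at 144 h + 1 min |
| Confirmed WHF at 100 h, last assessment 144 h | Event at 100 h + 1 min | Event at 100 h + 1 min |
| No event, last assessment 144 h | Censored at 144 h + 1 min | Censored at 144 h + 1 min |

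The rules part only when the recorded event falls after the last WHF assessment. Carrying over the primary-endpoint wording gives the Table 5.2-4 result in all three rows.

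**Step 2. A cross-check inside the SAP.** Table 5.2-8, for time to first re-hospitalization, counts the first patient's readmission as an event, because it falls within 30 days. The same report could count that readmission there and leave it out of the Day 14 composite.

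**Step 3. Illustrative size.** Number affected = N × L × r, where

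- N = 3,183 (SAP section 2.3);
- L = share lost before the Day 14 assessment, assumed 0.5% to 3%;
- r = share of those with an HF readmission on record after the last WHF assessment, assumed 2% to 10%.

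Low: 3,183 × 0.005 × 0.02 = 0.3. Middle: 3,183 × 0.01 × 0.05 = 1.6. High: 3,183 × 0.03 × 0.10 = 9.5.

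For scale, protocol section 1.1 quotes Day 14 WHF rates of 15.7% (placebo) and 11.4% (serelaxin) from the earlier phase III study. With 2:1 allocation the arms are 3,183 / 3 = 1,061 and 2 × 1,061 = 2,122. Expected WHF events are 1,061 × 0.157 + 2,122 × 0.114 = 166.6 + 241.9 = 408.5. The range is then 0.3 / 408.5 = 0.1% to 9.5 / 408.5 = 2.3%. The 408.5 covers WHF only, without readmissions, and assumes that the earlier rates carry over.

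**The case against.** **The sentence may only restate the censoring time of event-free patients.** It follows the footnote of Table 5.2-4, so this is a possible intention. Table 5.2-4 already handles those patients, however, so on this reading the sentence adds nothing. The wording does not say it, and the primary-endpoint text shows that the SAP can state that rule plainly.

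**A recorded readmission may bring its own WHF record.** The SAP collects WHF from Day 6 to Day 14 on the heart failure details page, which is also completed when a re-hospitalization is for HF. A WHF assessment made during or after the readmission would save the event. This stands and narrows the problem. It does not close it, because the SAP does not say whether that page counts as a last assessment.

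**A missed Day 14 visit is not the same as loss.** All patients are due a Day 30 call that covers repeat hospitalization (protocol section 3.1). This also stands: the rule touches only patients who are truly lost, and the SAP does not define when that is.

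**A common cut-off for events and time at risk can be defended.** Counting events after the last assessment, while censoring event-free patients at it, lets an event extend follow-up. But Table 5.2-4 and the primary-endpoint rule both accept that asymmetry, so it cannot explain an exception for this one endpoint.

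**Two endpoints may have different rules.** True. The difference from the primary endpoint is not a contradiction in itself; the conflict with Tables 5.2-3 and 5.2-4 and with the protocol is.

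A reader might also infer that observed events become event-free time, or that the result is biased towards one arm. The documents support neither. In the survival analyses the patient leaves the risk set at the last assessment, and no later time is credited. Only the descriptive proportions show the patient without an event. The rule is the same in both arms, and nothing in the documents shows differential loss.

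**Conclusion.** The conflict is real and narrow. It applies to patients lost to follow-up whose event, in practice mainly an HF readmission, is on record but dated after the last WHF assessment. Deaths are less exposed, since a patient known to have died would not normally be classed as lost.

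The sentence can lower event counts and cannot raise them. A few events is a reasonable expectation, but that rests wholly on the assumed loss and readmission rates. The censoring time depends on the last assessment: about 120 h if that was Day 5, later if discharge was later. The effect on the treatment comparison cannot be given a direction. The planned sample size, the alpha level and the primary analysis are not touched. This is a minor point, worth settling before database lock so that the choice does not fall to the programmer.

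**What to change.** Replace the Day 14 lost-to-follow-up sentence in SAP section 5.2 with: *For a patient lost to follow-up, a WHF event, death or HF readmission recorded as occurring before the loss and within 336 hours is counted, subject to Table 5.2-3; if there is none, the patient is censored at the last post-baseline assessment of in-hospital WHF, as in Table 5.2-4.*

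The same edit could say when a patient counts as lost, which the SAP leaves open.

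The cost is one sentence of SAP text. No new data, no protocol amendment and no change to the tables are needed.

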Data analysis	
The primary efficacy variable of the study is the time to in-hospital Worsening of Heart Failure (WHF) requiring rescue therapy or all-cause death through Day 5 post randomization.
 
The time to in-hospital WHF/all cause death will be computed as the number of hours from randomization to the earlier of the onset of WHF or death. Subjects without an event will be censored at the earlier of the last assessment or 120 hours after randomization.
 
The primary statistical hypothesis is $H_0: \lambda_2/\lambda_1 \geq 1$ versus the one-sided alternative $H_A: \lambda_2/\lambda_1 < 1$, where λ_1 and λ_2 are the hazard rates for WHF or all cause death in the Standard of Care group and serelaxin group, respectively. The hypothesis will be tested based on the Full Analysis Set (FAS) with a Gehan's generalized Wilcoxon test at a significance level of 0.025 (one-sided).
  
Time to in-hospital WHF/all cause death/readmission through Day 14 post randomization will be analyzed using survival analysis as in the primary analysis.
 
Treatments will be compared regarding proportions of patients with persistent signs or symptoms of HF/ not showing an improvement vs.
 

	baseline through Day 5 by means of Chi square test / Fisher Exact test. Index length of stay, overall and by location, in the two treatment groups will be compared using a Wilcoxon rank-sum test.
Key words	Acute Heart Failure, Worsening of Heart Failure, standard of care.

1 Introduction

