9.5.1 Efficacy variables

Time to in-hospital WHF/All-cause death/readmission for heart failure through Day 14 post randomization

Time to in-hospital WHF/all-cause death/readmission for heart failure through Day 14 post randomization will be analyzed using survival analysis.

The time to in-hospital WHF/all-cause death/readmission will be computed as the number of hours from the randomization to the earlier of the onset of in-hospital WHF or death or readmission. The onset of in-hospital WHF through Day 14 will be the first assessment point,

in terms of date and time, at which the investigator reported worsening heart failure (either during the initial hospitalization or re-hospitalization for heart failure). Subjects without an event will be censored at the earlier of the last assessment or 336 hours after randomization.

Treatment groups will be compared with a Gehan's generalized Wilcoxon test.

The Kaplan-Meier estimates of the survival functions for each treatment group will be plotted. The Kaplan-Meier estimates of the cumulative event rate will also be presented in tables by treatment group for each day and also by time interval.

Absolute frequencies and proportions of patients with in-hospital WHF/all-cause death/readmission through Day 14 in each treatment group will be also provided.

Persistent signs or symptoms of HF/ non-improvement

Absolute frequencies and proportions of patients with persistent symptoms or signs of HF / not showing an improvement vs. baseline through Day 5 (persisting need of IV therapy for HF) and at discharge in each treatment group will be provided, together with standard errors, asymptotic (Wald) and exact (Clopper-Pearson) confidence limits. The rates in the two groups will be compared by means of Chi square test at each time point. In case of cell frequencies less than 5, Fisher Exact test will be used. A time-to-event analysis will be applied to provide treatment comparisons. Hazard ratios of being a responder for each of the signs and symptoms variables will be estimated using a Cox regression model with treatment as factor.

Renal deterioration

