Renal deterioration will be assessed as the proportion of patients with an increase of ≥ 0.3 mg/dL from screening in serum creatinine levels. Absolute frequencies and proportions of patients with renal deterioration at each day until Day 5, at discharge and at Day 14 in each treatment group will be provided, together with standard errors, asymptotic (Wald) and exact (Clopper-Pearson) confidence limits. The rate of renal deterioration in the two groups will be compared by means of Chi square test at each time point. In case of cell frequencies less than 5, Fisher Exact test will be used.

Index length of hospital stay

Index length of hospital stay (in hours) will be defined as the index discharge date and time minus the index hospitalization start date and time.

Subjects still in the hospital at Day 30 will be censored at the end of Day 30. Subjects who die during the initial hospitalization will be assigned the maximum length of stay (including those censored at Day 30) plus 24 hours. Treatment groups will be compared using a Wilcoxon rank-sum test. Descriptive statistics by treatment group will be presented. Analysis will be done overall and by location (e.g. ICU, CCU, cardiology department).

Death through Day 30

The time (in days) from randomization to the event will be used for analysis. Subjects without an event will be censored at the earlier of the last contact date or Day 30. Treatment groups will be compared using a generalized Wilcoxon test. The Kaplan-Meier estimates of the survival functions for each treatment group will be plotted.

Re-hospitalization post-discharge

The number of re-hospitalizations per patients by treatment group will be described. Treatment groups will be compared using a Wilcoxon rank-sum test. The number of patients with 1, 2, ≥ 2 re-hospitalization will be summarized and treatment groups will be compared with a Chi-Square test. In case of cell frequencies less than 5, Fisher Exact test will be used.

Time to first re-hospitalization (in days) will be defined as the re-hospitalization date minus the randomization date. Subjects still in hospital at Day 30 will be censored at Day 30. Subjects who die when not hospitalized will be assigned as the date of death as their time to re-hospitalization. Treatment groups will be compared using a generalized Wilcoxon test. The Kaplan-Meier estimates for each treatment group will be plotted. Descriptive statistics by treatment group will be presented.

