1.2. SECONDARY OBJECTIVES

The secondary objectives of the study are the following:

- To assess the effect of serelaxin as add-on therapy to SOC versus SOC alone in reducing in-hospital WHF requiring rescue therapy or all cause death or readmission for heart failure, from randomization through Day 14.
- To assess the effect of serelaxin as add-on therapy to SOC versus SOC alone in reducing the number of patients with persistent symptoms or signs of Heart Failure (HF) / not showing an improvement versus baseline conditions from randomization through Day 5 (persisting need of IV therapy for HF).
- To evaluate the effect of serelaxin as add-on therapy to SOC versus SOC alone in reducing the rate of renal deterioration (defined as ≥ 0.3 mg/dL increase in serum creatinine), from randomization through Day 5.
- To evaluate the effect of serelaxin as add-on therapy to SOC versus SOC alone in modifying the index length of stay (LOS) by location (e.g., ICU, CCU, cardiology department) in days and hours (ICU).
- To evaluate the safety and tolerability of intravenous serelaxin in Acute Heart Failure (AHF) patients during a period of 30 days following exposure.
- To collect data on health-related quality of life (HRQoL) and economic burden to provide a more comprehensive analysis of the burden of HF, beyond the clinical outcomes.

	<h1>Statistical Analysis Plan</h1>
	Sponsor: NOVARTIS

Protocol number: CRLX030A3301

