Persistent signs and symptoms of HF/non-improvement

The number of patients with persistent symptoms or signs of HF / not showing an improvement versus baseline conditions through Day 5 (persisting need of IV therapy for HF) will be evaluated.

Patients with persistent symptoms or signs of HF / not showing an improvement versus baseline conditions through Day 5 are those patients who take any IV therapy for HF at each assessment time point as reported in the eCRF sections “IV Loop Diuretic Medication for Heart Failure” and “IV Medications Other than Loop Diuretics”.

Moreover, the investigator or appropriate qualified designee evaluates the symptoms and signs of heart failure, including dyspnea on exertion or at rest, orthopnea, rales, jugular venous pulse (JVP) and peripheral edema. These evaluations are performed at baseline, 6, 12, 24 and 48 hours from start of study drug infusion, daily through index hospitalization, at Day 5, at discharge and then at Day 14 for the serelaxin arm. For patients in the SOC arm, relevant evaluations are performed at baseline, at 6, 12, 24 and 48 hours from randomization, daily through index hospitalization, at Day 5, at discharge, and then at Day 14.

These evaluations should be done at approximately the same time of the day, each day, in the same position and hospital/clinic setting, preferably by the same assessor.

Renal deterioration

Renal deterioration is defined as an increase of ≥ 0.3 mg/dL from screening in serum creatinine levels. Rate of renal deterioration at 24 hours, at 48 hours, at Day 5, at discharge, and at Day 14 post randomization will be evaluated.

Serum creatinine evaluations are performed locally at screening, at 24 and 48 hours, at Day 5, at discharge, and then at Day 14 post randomization.

Index length of hospital stay

Index length of hospital stay (in hours) is defined as the index hospitalization discharge date and time minus the index hospitalization admission date and time + 1 minute.

Index length of hospital stay, from admission to discharge, will be evaluated by location (emergency ward, emergency care unit, etc.).

Index hospitalization details are collected in eCRF at Screening, Day 5, discharge visit, Day 14 and Day 30 post randomization.

	Statistical Analysis Plan
	Sponsor: NOVARTIS Protocol number: CRLX030A3301

Death through Day 30

All deaths (adjudicated or not) occurring from randomization through Day 30 will be used in the analysis.

Re-hospitalization post-discharge

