Absolute frequencies and proportions of patients with persistent symptoms or signs of HF / not showing an improvement at any visit vs. baseline (persisting need of IV therapy for HF) in each treatment group will be provided, and also at each assessment time point (24 hours, 48 hours, Day 3, Day 4) through Day 5 and at discharge, together with standard errors, asymptotic (Wald) and exact (Clopper-Pearson) confidence limits. The rates in the two groups will be compared by means of Chi square test at each time point. In case of cell frequencies less than 5, Fisher’s Exact test will be used.

Patients with persistent symptoms or signs of HF / not showing an improvement versus baseline conditions at each assessment time point are those patients who take any IV therapy for HF at the assessment time point as reported in the eCRF sections “IV Loop Diuretic Medication for Heart Failure” and “IV Medications Other than Loop Diuretics”.

Improvement in signs or symptoms of HF

A time-to-event analysis through Day 14 will be performed. Hazard ratios of being a responder for each of the signs and symptoms variables (response is defined as ≥ 1 point improvement from baseline) will be estimated using a Cox regression model with treatment as a factor.

Treatment groups will be compared with a Gehan’s generalized Wilcoxon test. The Kaplan-Meier estimates of the cumulative event rate will also be presented by treatment group.

One or more point improvement will be defined as a reduction from baseline of at least one point in the specific sign/symptom according to the score defined in the table below.

Statistical Analysis Plan

Sponsor: NOVARTIS

Protocol number: CRLX030A3301

Table 5.2-5: Scores for the definition of improvement

	Categorical value	Numerical value
Dyspnea on exertion	None	0
	Mild	1
	Moderate	2
	Severe (including dyspnea at rest)	3
Orthopnea	None	0
	1 pillow (10cm)	1
	2 pillows (20cm)	2
	>30 degrees	3
Edema	0	0
	1+	1
	2+	2
	3+	3
Rales	No rales	0
	Rales <1/3	1
	Rales 1/3-2/3	2
	Rales >2/3	3
Jugular venous pulse (JVP)	<6cm	0
	6-10cm	1
	>10cm	2
Body weight increase	No	0
	Yes	1

The scores will be presented as both categorical and continuous (i.e., numerical values in Table 5.2-5) statistics. Change from baseline will be computed as the baseline value subtracted from the post baseline values. Cross tabulation of categorical values at baseline and at each assessment time point will be presented by treatment group.

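### Renal deterioration through Day 5 is tested only visit by visit, and persistent heart failure through Day 5 has no single tested variable and no stated denominator for discharged patients

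*SAP*

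**What the plan says.** **Renal deterioration.** The objective in SAP 1.2 is to reduce the rate of deterioration, a rise of 0.3 mg/dL or more ("increase in serum creatinine), from randomization through Day 5"). Protocol 9.5.1 reports "patients with renal deterioration at each day until Day 5, at discharge and at Day 14", with a chi-square test at each time point. SAP 4.1 states: "Rate of renal deterioration at 24 hours, at 48 hours, at Day 5, at discharge, and at Day 14 post randomization will be evaluated". SAP 5.2 tests each of these assessments separately.

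Two cumulative summaries exist, both in SAP 5.3. The laboratory tables count patients with a creatinine rise of 0.3 mg/dL or more at any post-baseline visit. The events-of-interest tables count renal impairment reported as an adverse event through Day 5 and Day 14. Neither has a stated test, and all SAP 5.3 analyses use the Safety set.

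**Persistent heart failure.** The objective again runs through Day 5. The protocol synopsis compares proportions of patients without improvement vs. "baseline through Day 5 by means of Chi square test / Fisher Exact test". Protocol 9.5.1 says: "The rates in the two groups will be compared by means of Chi square test at each time point". SAP 4.1 describes the patients as those "who take any IV therapy for HF at each assessment time point as reported in the eCRF sections" for IV medication. SAP 5.2 first gives an overall count of patients "not showing an improvement at any visit vs. baseline (persisting need of IV therapy for HF"), then a visit-level status: patients with persistent symptoms or signs "are those patients who take any IV therapy for HF at the assessment time point as reported in the eCRF sections". Chi-square tests are stated per time point: 24 h, 48 h, Day 3, Day 4, Day 5 and discharge.

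**Rules that bear on discharge.** Under SAP 2.6 daily visits stop at discharge. Protocol 3.1 brings patients discharged early back at Days 5 and 14. SAP 5.1 (General methodology) includes patients by available assessments without imputation. SAP 5.1 (Concomitant treatments) computes medication percentages over everyone in the analysis population.

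**The concern.** For the renal objective, the quantity named is whether a patient deteriorated at some point in the first five days. The plan never tests that quantity in the Full Analysis Set (FAS). A reader of the report would have three visit-level p-values inside the window and an untested count from another population and an open-ended period.

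For persistent heart failure, two programmers could follow the text and build different patient-level variables, and the overall count has no stated test. In addition, nothing says whether a patient already at home on Day 3 or Day 4 is left out or counted as off therapy. Protocol 1.1 reports that serelaxin shortened the index stay in the earlier phase III trial. A rate computed only among patients still in hospital is therefore conditioned on a post-randomization event that treatment is expected to change, and the randomized comparison is lost at those visits.

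**Working it through.** The documents give no expected rate for either variable, so there is no plan figure to reproduce. All rates below are assumptions.

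**1. Visit-wise renal rates do not give the renal objective.** Within the window creatinine is scheduled at 24 h, 48 h and Day 5 (SAP 4.1), plus discharge if that comes earlier. The protocol's daily rates until Day 5 therefore have no scheduled sample on Days 3 and 4. For visit rates p1, p2 and p3, the proportion with a rise at any of the three visits lies between max(p1, p2, p3) and p1 + p2 + p3:

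| Assumed rates (24 h / 48 h / Day 5) | Lower bound | Upper bound |
|---|---|---|
| 6 / 8 / 10% | 10% | 24% |
| 10 / 13 / 15% | 15% | 38% |
| 15 / 18 / 20% | 20% | 53% |

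The three visit results leave the cumulative proportion in each arm undetermined. It must be computed per patient.

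**2. The two conventions for a discharged patient disagree.** Take a patient discharged on Day 2.
- Available assessments: there is no Day 3 or Day 4 visit, so the patient is dropped.
- Medication convention: the denominator is the analysis population, so the patient stays and counts as not on IV therapy.

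The persistent-heart-failure text in SAP 5.2 does not choose. Neighbouring parts of SAP 5.2 do state a denominator: the analysis population for the Day 14 composite, and non-missing information for the signs and symptoms.

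**3. Size of the distortion if discharged patients are dropped.** Inputs: 3,183 patients (SAP 2.3) randomized 2:1 (SAP 2.2), so 2,122 serelaxin and 1,061 standard of care (SOC). Assume that 25% of each arm is truly on IV therapy at Day 4, that there is no treatment difference, and that all discharged patients are off IV therapy. With a fraction d discharged and dropped:

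- Observed rate = 0.25 / (1 − d)
- SE = √[r₁(1 − r₁)/n₁ + r₂(1 − r₂)/n₂], where each n is the arm size × (1 − d)

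| Discharged, SOC vs serelaxin | Rate, SOC | Rate, serelaxin | Spurious difference | SE | Ratio |
|---|---|---|---|---|---|
| 10% vs 12% | 27.8% | 28.4% | 0.6 points | 1.79 | 0.35 |
| 10% vs 15% | 27.8% | 29.4% | 1.6 points | 1.80 | 0.91 |
| 20% vs 25% | 31.3% | 33.3% | 2.1 points | 1.98 | 1.05 |

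The direction is against serelaxin in every row. If discharged patients stay in the denominator as not persistent, both arms show 25% and the distortion is zero.

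**4. Deaths.** Assume 2% dead on SOC and 1% on serelaxin, 25% failing overall, and all dying patients counted as failures in the reference. Dropping deaths shifts the comparison by (1 − 0.25) × 1 = 0.75 points; counting them as not persistent shifts it by 1.0 point. With SE = √[0.25 × 0.75 × (1/1061 + 1/2122)] = 1.63 points, these are 0.46 and 0.61 SE.

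**The case against.** The strongest reply is that the SAP does what the protocol asks. Protocol 9.5.1 specifies visit-wise rates and tests for both variables, and SAP 5.1 says that analyses follow protocol Section 9. That is correct: this is not a departure from the protocol. The gap between the objective and the analysis is in both documents.

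Several stronger readings are tempting but not supported.

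- A reader might infer that SAP 4.1 and 5.2 flatly contradict each other, one requiring IV therapy at every visit and the other at any one visit. But "each" can be distributive (status determined visit by visit), and a patient not improving at any visit can mean one improving at no visit. The wording is ambiguous, so a contrast between all-visit and any-visit rates does not measure a defect.
- A reader might infer that the overall count in SAP 5.2 has no time limit. Protocol 9.5.1, which SAP 5.1 adopts, largely supplies the Day 5 limit.
- A reader might see a multiplicity failure in the repeated tests. SAP 5.2 says that secondary endpoints are not adjusted, so no error control is claimed that could be breached.
- A reader might conclude that death must enter the main definition, because length of stay and diuretic dose have death rules. The assumed effect is small, and such a composite would overlap the primary endpoint.

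It is also fair that the discharge example is constructed (more serelaxin discharges but equal overall IV use) and that its bias cannot produce a false claim of benefit. The rationale for Protocol Amendment 2 expects most discharges after Day 5, which favours the smaller figures. Other information is available too: SAP 5.2 analyses time to improvement in each sign and symptom, and Protocol 5.5.7 records concomitant treatment to Day 30, so a missed Day 5 visit need not leave only survival status.

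What stands is the untested cumulative renal outcome, the unnamed persistent-heart-failure comparison, and the unresolved Day 3 and Day 4 denominator.

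**Conclusion.** The point holds as a gap in specification for two unadjusted secondary objectives. The renal part needs no assumed rates: no planned test uses deterioration at any time through Day 5. For persistent heart failure, the text does not identify one patient-level variable and test, and the SAP's own conventions conflict on discharged patients. Dropping them would distort the Day 4 rate by about 0.6 to 2.1 points against serelaxin (0.35 to 1.05 SE). This rests on assumed discharge fractions, 25% IV use in both arms, and no IV therapy after discharge; the lower end is the more plausible. Day 5 is less exposed because discharged patients are due to return. The primary analysis is unaffected. This is a cheap improvement worth making before database lock, especially in an open-label trial.

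**What to change.** **Renal, SAP 5.2.** Add one FAS comparison of the proportion with a creatinine rise of 0.3 mg/dL or more from screening at any scheduled assessment through Day 5. Report by arm the number with no post-screening value. Add a sensitivity analysis counting death as failure. Keep the visit-wise tests as supportive.

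**Persistent heart failure, SAP 4.1 and 5.2.** Use one wording in both sections and name one variable and test for the objective, for example IV heart-failure therapy at the Day 5 assessment. Status at the end of the window suits a persisting need, whereas renal deterioration is an event that can occur at any point in it. At Day 3 and Day 4, keep discharged patients not on IV therapy in the FAS denominator as not persistent. Report deaths and missed Day 5 visits by arm, with a sensitivity analysis counting them as persistent, and leave death out of the main definition.

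**Cost.** SAP wording and slightly more programming on data already collected. The protocol's visit-wise tests are still run, so Protocol 9.5.1 can stand; a written amendment (Protocol 11.1) is needed only if those tests are formally downgraded or death is added to the protocol definition. The downside is the assumption that patients discharged without recorded IV therapy are off it.
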